#### 14.1.2 ORA CALIBRA® OCULAR DISCOMFORT SCALE

Ocular discomfort scores will be subjectively graded by the subjects using the Ora Calibra® Ocular Discomfort Scale at all scheduled visits. The ocular discomfort scale ranges from 0 to 4 [REDACTED]

[REDACTED]  
 [REDACTED].

Changes from baseline in the pre-CAE® Ocular Discomfort Scale will be summarized at Visit 6 (Day 57 ± 3) by treatment group for the study eye using quantitative summary statistics. Changes from baseline will be compared between each dose of 0.25% and 0.10% HL036 Ophthalmic Solution and placebo using an ANCOVA model that adjust for baseline and site. In addition, the study site by treatment interaction will be explored in a separate model to evaluate how the treatment effect may differ across study sites. In the case of a significant interaction at the 0.05 level, analyses will be performed by site to understand how the treatment effect differs across sites. The differences in means, two-sided 95% confidence intervals (CIs) for the difference in means and p-values will be reported. Pairwise t-tests from the ANCOVA model will be used to compare treatment and placebo groups. In addition, subjects in either active treatment group will be compared to the placebo group using a separate ANCOVA model. T-tests and Wilcoxon rank sum tests will also be conducted as sensitivity analyses to assess robustness of the results.

The primary analysis will use MCMC imputation on the ITT population at Visit 6 (Day 57 ± 3). SAS code for the multiple imputation analysis will resemble the code in Section 14.1.1. for pre-CAE® inferior fluorescein staining. Sensitivity analyses will be performed on the ITT and PP populations using observed data only, and on the ITT population using LOCF methodology and pattern mixture model imputation. The sensitivity analyses will include comparisons between treatment and placebo groups using ANCOVA models adjusting for site and baseline and t-tests. Observed data only (ITT and PP) and LOCF analyses will also include Wilcoxon rank sum tests.

Changes from baseline in the pre-CAE® Ocular Discomfort Scale in the study eye will be displayed graphically in a bar chart with standard error bars by visit and treatment group.

#### 14.2 Secondary Analyses

The continuous and ordinal secondary efficacy variables collected at each visit will be summarized descriptively (n, mean, standard deviation, median, min and max) by visit and treatment group. Change scores from pre- to post-CAE® will be calculated as post-CAE® score – pre-CAE® score. Changes from baseline will also be summarized descriptively by visit and treatment group. Summaries will also be provided for all subjects in either active treatment group. No imputation will be performed for secondary efficacy variables. Analyses will be performed on the ITT population with observed data only. All exploratory measures will also be presented in subject listings.

The following secondary efficacy endpoints will be tested:

- Fluorescein staining (Ora Calibra® scale); regions: central, superior, inferior, temporal, nasal, corneal sum, conjunctival sum, and total eye score);

- Lissamine green staining (Ora Calibra® scale); regions: inferior, superior, central, temporal, nasal, conjunctival sum);
- TFBUT;
- Conjunctival Redness;
- Unanesthetized Schirmer's Test;
- Ora Calibra® Ocular Discomfort Scale;
- Ora Calibra® Ocular Discomfort & 4-Symptom Questionnaire;
- Visual Analogue Scale;
- OSDI®;
- Ora Calibra® Drop Comfort assessment;
- Daily Diary;
- Tear Mediators

#### 14.2.1 FLUORESCEIN STAINING

Corneal and conjunctival fluorescein staining will be performed at all scheduled visits, on both eyes and graded using the Ora Calibra® Corneal and Conjunctival Staining Scale. Both pre- and post-CAE® assessments will be made at Visits 1, 2, 4, 5, and 6. The scale will grade the cornea and conjunctiva by five regions: inferior, superior, central, temporal, and nasal. The Ora Calibra® Corneal and Conjunctival Staining Scale ranges from 0 to 4 [REDACTED], where grade 0 = none, [REDACTED] and 4 = severe.

Fluorescein staining scores will be summarized by visit, time point (pre- and post-CAE®), and region (5 regions, plus corneal sum, conjunctival sum, and total scores) for the study eye using quantitative summary statistics. The corneal sum score will be the sum of scores from the inferior, superior, and central regions. The conjunctival sum score will be the sum of scores from the nasal and temporal regions. The total score will be the sum of scores from all five regions.

Pairwise two-sample t-tests will be employed to compare treatment and placebo means at each visit and time point. Comparisons between treatment groups and between all active groups and placebo will also be conducted. The differences in means, two-sided 95% confidence intervals (CIs) for the difference in means and p-values will be reported. Wilcoxon rank sum tests will also be conducted. Analyses will be performed on the ITT population with observed data only.

Changes from baseline will be compared between treatment groups using ANCOVA models that adjust for baseline and site. The differences in means, two-sided 95% confidence intervals (CIs) for the difference in means and p-values will be reported. T-tests and Wilcoxon rank sum tests will also be conducted. Analyses will be performed on the ITT population with observed data only.

#### 14.2.2 LISSAMINE GREEN STAINING

Corneal and conjunctival lissamine green staining will be performed at all visits, on both eyes and graded using the Ora Calibra® Corneal and Conjunctival Staining Scale. Both pre- and post-CAE® assessments will be made at Visits 1, 2, 4, 5, and 6. The scale will grade the cornea and conjunctiva by five regions: inferior, superior, central, temporal, and nasal. The Ora Calibra® Corneal and Conjunctival Staining Scale ranges from 0 to 4 [REDACTED], where grade 0 = none, [REDACTED] and 4 = severe.

Lissamine green staining scores will be summarized by visit, time point, and region (5 regions, plus corneal sum, conjunctival sum, and total scores) for the study eye using quantitative summary statistics. The corneal sum score will be the sum of scores from the inferior, superior, and central regions. The conjunctival sum score will be the sum of scores from the nasal and temporal regions. The total score will be the sum of scores from all five regions.

Pairwise two-sample t-tests will be employed to compare treatment and placebo means at each visit and time point. Comparisons between treatment groups and between all active groups and placebo will also be conducted. The differences in means, two-sided 95% confidence intervals (CIs) for the difference in means and p-values will be reported. Wilcoxon rank sum tests will also be conducted. Analyses will be performed on the ITT population with observed data only.

Changes from baseline will be compared between treatment groups using ANCOVA models that adjust for baseline and site. The differences in means, two-sided 95% confidence intervals (CIs) for the difference in means and p-values will be reported. T-tests and Wilcoxon rank sum tests will also be conducted. Analyses will be performed on the ITT population with observed data only.

#### 14.2.3 TEAR FILM BREAK-UP TIME (TFBUT)

TFBUT will be measured at all scheduled visits on both eyes. Both pre- and post-CAE® assessments will be made at Visits 1, 2, 4, 5, and 6. For each eye, two measurements will be recorded in seconds and averaged unless the two measurements are >2 seconds apart and are each <10 seconds, in which case, a third measurement will be taken and the two closest of the three will be averaged and used for analyses. If the differences between two sequential pairs of measurements are the same, e.g., 3, 6, 9 seconds, then the median of the three readings will be used for analysis.

TFBUT will be summarized by visit, time point, and treatment group using quantitative summary statistics. Change from baseline will also be summarized.

Pairwise two-sample t-tests will be employed to compare treatment and placebo means at each visit and time point. Comparisons between treatment groups and between all active groups and placebo will also be conducted. The differences in means, two-sided 95% confidence intervals (CIs) for the

difference in means and p-values will be reported. Wilcoxon rank sum tests will also be conducted. Analyses will be performed on the ITT population with observed data only.

Changes from baseline will be compared between treatment groups using ANCOVA models that adjust for baseline and site. The differences in means, two-sided 95% confidence intervals (CIs) for the difference in means and p-values will be reported. T-tests and Wilcoxon rank sum tests will also be conducted. Analyses will be performed on the ITT population with observed data only.

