The OSDI® is assessed on a scale of 0 to 100, with higher scores representing greater disability. The index demonstrates sensitivity and specificity in distinguishing between normal subjects and patients with dry eye disease. The OSDI® is a valid and reliable instrument for measuring dry eye disease (normal, mild to moderate, and severe) and effect on vision-related function.

Assessing Your Patient's Dry Eye Disease^{1,2}

[figure not shown]
Use your answers D and E from side 1 to compare the sum of scores for all questions answered (D) and the number of questions answered (E) with the chart below.* Find where your patient's score would fall. Match the corresponding shade of red to the key below to determine whether your patient's score indicates normal, mild, moderate, or severe dry eye disease.

1. Data on file, Allergan, Inc.

Ora Calibra® Conjunctival Redness Scale for Dry Eye

Tear Film Break-Up Time (TFBUT)®

The examiner will instill [REDACTED] solution into the inferior conjunctival cul-de-sac of each eye. To thoroughly mix the fluorescein with the tear film, the subject will be instructed to blink several times. In order to achieve maximum fluorescence, the examiner should wait approximately 30 seconds after instillation before evaluating TFBUT.

With the aid of a slit-lamp, the examiner will monitor the integrity of the tear film, noting the time it takes to form micelles from the time that the eye is opened. TFBUT will be measured in seconds using a stopwatch and a digital image recording system for the right eye followed by the left eye. A Wratten #12 yellow filter will be used to enhance the ability to grade TFBUT.

For each eye, 2 measurements will be taken and averaged unless the 2 measurements are > 2 seconds apart and are each < 10 seconds, in which case, a third measurement would be taken and the 2 closest of the 3 would be averaged.

Fluorescein Staining

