### 3.2 Secondary Efficacy Endpoints

- Fluorescein staining by region: central, superior, inferior, temporal, nasal and corneal sum as assessed by the Ora Calibra® Corneal and Conjunctival Staining Scale for Grading of Fluorescein Staining at all time points

- Lissamine green staining by region: central, superior, inferior, temporal, nasal, and conjunctival sum as assessed by the Ora Calibra® Corneal and Conjunctival Staining Scale for Grading of Lissamine Staining at all time points
- TFBUT® at all timepoints assessed
- Conjunctival redness as assessed by the Ora Calibra® Conjunctival Redness Scale for Dry Eye at all timepoints assessed
- Schirmer's Test (unanesthetized) at all timepoints assessed
- Symptoms as assessed by the Ora Calibra® Ocular Discomfort Scale and Ora Calibra® Ocular Discomfort and 4-Symptom Questionnaire at all timepoints
- Visual Analog Scale (VAS) Ocular Discomfort at all timepoints assessed
- OSDI® at all timepoints assessed
- Drop comfort as assessed by the Ora Calibra® Drop Comfort Scale, and the Ora Calibra® Drop Comfort Questionnaire at all timepoints assessed
- Daily diary
- Tear mediators

Change from baseline and change from pre- to post-CAE® will also be assessed where appropriate.

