### 9.4 Data Analysis Conventions

All data analysis will be performed by SDC after the study is completed and the database has been locked and released for unmasking. Statistical programming and analyses will be performed using SAS® Version 9.4 or higher. Output will be provided in RTF (Rich Text Format) for tables and PDF (Portable Document Format) for tables, listings, and figures using landscape orientation. All study data will be listed by subject, treatment, and visit (as applicable) based on all enrolled subjects unless otherwise specified.

All summaries will be presented by treatment group and visit where appropriate, unless otherwise specified. Summaries will be provided for demographics, baseline medical history, concurrent therapies, and subject disposition. For the purpose of summarization, medical history, concurrent therapies, and adverse events will be coded to Medical Dictionary for Regulatory Activities (MedDRA) and World Health Organization (WHO) Drug dictionaries, as appropriate.

Summaries for continuous and ordinal variables will include the number of observations (n), arithmetic mean, standard deviation (SD), median, minimum, and maximum. Minima and maxima will be reported with the same precision as the raw values; means and medians will be presented to one additional decimal place than reported in the raw values. Standard deviations will be presented to two additional decimal places than reported in the raw values. Summaries for discrete variables will include frequency counts and percentages. All percentages will be rounded to one decimal place (i.e., XX.X%).

All statistical tests will be two-sided with a significance level of 0.05 ( $\alpha = 0.05$ ) unless otherwise specified. Confidence intervals (CI) for differences between treatment groups will be two-sided at 95% confidence levels where appropriate. All p-values will be rounded to four decimal places; p-values

less than 0.0001 will be presented as "<0.0001"; p-values greater than 0.9999 will be presented as ">0.9999".

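### When a third TFBUT reading is taken, the median of the three would be more precise than the closest-pair average in SAP 14.2.3

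*SAP*

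**What the plan says.** SAP 14.2.3 takes two TFBUT readings per eye, which are "averaged unless the two measurements are >2 seconds apart and are each <10 seconds". If both conditions are met, "a third measurement will be taken and the two closest of the three will be averaged and used for analyses". Where the two gaps between the three readings are equal, as in the SAP's example of 3, 6 and 9 s, "then the median of the three readings will be used for analysis".

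Protocol Appendix 2 has the same trigger and the same rule, "a third measurement would be taken and the 2 closest of the 3 would be averaged", but no provision for equal gaps.

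TFBUT is a secondary efficacy endpoint (SAP 3.2: "TFBUT® at all timepoints assessed"). Under SAP 14.2.3 it is compared between arms at each visit and time point, and change from baseline is analysed by ANCOVA adjusting for baseline and site. Pre-CAE TFBUT is also a reported baseline characteristic (SAP 11.2). Neither document gives a within-eye SD, an error distribution, a rate of faulty readings or a reason for the rule.

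**The concern.** A third reading should steady a value that the first two leave in doubt. This rule uses it mainly to decide which reading to drop. With only three readings, two that lie close together are often a chance cluster on one side of the true value, so averaging them can pull the result away from the truth. The recorded value can also jump when the third reading barely changes.

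The noise enters both baseline and follow-up values of TFBUT in every arm. What is at stake is some precision in one secondary sign and in its baseline covariate.

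**Working it through.** **Inputs.** From the documents: the trigger (difference above 2 s, both readings below 10 s), the closest-pair average and the median for equal gaps. Assumed, because the documents are silent: a true value of 5 s, the within-eye SD and the error shape, with readings independent within an eye. The plan states no figure for TFBUT precision, so there is none to reproduce.

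**1. The jump, with no distributional assumption.** Take first readings of 3 and 6 s, which trigger a third.

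| Third reading | Gaps | Plan records | Median of three |
|---|---|---|---|
| 8.9 s | 3.0, 2.9 | (6 + 8.9)/2 = 7.45 s | 6 s |
| 9.0 s | 3.0, 3.0 | 6 s (equal-gap clause) | 6 s |
| 9.1 s | 3.0, 3.1 | (3 + 6)/2 = 4.5 s | 6 s |

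Raising the third reading by 0.2 s lowers the recorded value by 7.45 − 4.5 = 2.95 s. The equal-gap clause repairs only the single point between the two outcomes.

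**2. Normal error, no trigger, unit variance.** Variance is 0.638 for the closest pair, 0.500 for the mean of two, 0.448 for the median of three and 0.333 for the mean of three.

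**3. Normal error with the plan's trigger, eyes that trigger only, SD 1.5 s (about 34% of eyes).** Mean squared error (MSE, s²) is 1.91 for the closest pair, 1.11 for the first two, 1.18 for the median and 0.74 for the mean of three. The median removes 1 − 1.18/1.91 = 38% of the closest-pair error. It is still slightly behind the first two alone.

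**4. Dependence on the SD.** Under normal error, the variance over all eyes under the plan, divided by that of the mean of two, is 1.01 at SD 0.5 s (0.5% of eyes trigger), 1.17 at 1 s (16%) and 1.25 at 1.5 s (34%).

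**5. Other error shapes.** MSE over all eyes, by simulating the exact rule with true value 5 s and two million sets of three readings per setting. A faulty reading is one drawn with the stated multiple of the SD.

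| Assumed error | Eyes triggering | First two only | Closest pair (plan) | Median of three | Mean of three |
|---|---|---|---|---|---|
| Normal, SD 1 s | 16% | 0.500 | 0.585 | 0.520 | 0.473 |
| Lognormal, CV 0.3 | 31% | 1.124 | 1.355 | 1.154 | 1.023 |
| Lognormal, CV 0.5 | 41% | 3.13 | 3.91 | 3.42 | 3.09 |
| SD 1 s, 5% faulty at 3 × SD | 19% | 0.701 | 0.695 | 0.619 | 0.609 |
| SD 1 s, 10% faulty at 5 × SD | 23% | 1.704 | 1.269 | 1.184 | 1.368 |
| SD 0.5 s, 10% faulty at 4 × SD | 7% | 0.313 | 0.207 | 0.200 | 0.242 |
| t with 3 df, scale 0.5 s | 7% | 0.375 | 0.285 | 0.274 | 0.310 |

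Three patterns follow:
- The closest pair loses to the first two under normal and lognormal error, and beats them once faulty readings or heavy tails are present.
- The mean of three is best under normal and lognormal error, but loses to the closest pair in the last three rows.
- The median beats the closest pair in every row.

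The median was also better in all the other settings run: normal SD 0.5 to 3 s, lognormal CV 0.2 to 0.5, 5% to 10% faulty readings at 3 to 5 × SD, t with 3 or 5 df, and spuriously low readings.

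**6. Effect on the trial comparison.** Let σ be the between-subject SD of true change, assumed 1.5 to 3 s, with independent reading error at baseline and follow-up. Confidence interval width for mean change scales with √(σ² + 2·MSE). Normal error, SD 1 s:
- Plan against first two only: √[(9 + 1.170)/(9 + 1.000)] = 1.009 at σ = 3 s, and √[(2.25 + 1.170)/(2.25 + 1.000)] = 1.026 at σ = 1.5 s.
- Median against plan: √[(9 + 1.040)/(9 + 1.170)] = 0.994 and √[(2.25 + 1.040)/(2.25 + 1.170)] = 0.981, so intervals are 0.6% to 1.9% narrower.

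At SD 0.5 s, the widening under the plan is 0.1% or less.

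**The case against.** The strongest defence is that a trigger for discordant readings is plausibly there to catch a faulty one, and dropping the outlying reading then makes sense. The figures bear this out: with 10% faulty readings at SD 0.5 s, the plan's error is 0.207 against 0.313 for the first two alone. A reader might infer from the normal-error results that the third reading always makes the data worse. The documents do not support that, because they give no error shape or rate of faulty readings, and the conclusion reverses across plausible assumptions. A reader might equally infer that all three readings should simply be averaged. That gives up the protection against faulty readings and can do worse than the plan (0.242 against 0.207 in the same setting).

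The defence does not extend to a comparison with the median, which keeps the protection and had lower error in the faulty-reading settings too. There the gain is small, though: 1 − 0.200/0.207 is about 3% of the error over all eyes.

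It is also fair to say that the two documents agree on the rule, that the SAP prespecifies the equal-gap case so nothing is left to the analyst, and that TFBUT is one of many secondary endpoints in a trial that SAP 9.5 describes as mainly exploratory. All of that stands and keeps the severity low.

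**Conclusion.** The point holds as a matter of efficiency. Once three readings exist, the median used them better than the closest pair in every setting tested. Whether the closest pair is also worse than stopping at two readings depends on the error distribution: yes under normal or lognormal error, no with faulty readings or heavy tails. The size depends on an unknown within-eye SD. Under normal error, the cost over all eyes relative to two readings runs from about 1% of variance at SD 0.5 s to 25% at SD 1.5 s.

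The rule is the same in all arms and the readings are masked, so the expected consequence is noise and not bias between arms. The coprimary endpoints and the success criterion are untouched.

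A reader might also see a fault in the trigger, since readings of 4 and 14 s are recorded as 9 s with no third reading. The arithmetic is right, but the documents do not explain the 10 s limit, so calling it an error is inference. It is a separate, smaller matter, and changing it would need extra readings.

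**What to change.** Before unmasking, change SAP 14.2.3 so that the median of the three readings is the analysis value whenever a third is taken. The separate equal-gap clause then becomes unnecessary. Align the sentence in protocol Appendix 2, or record the difference in SAP section 17, which currently reports no changes from the protocol's analyses.

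The cost is one SAP sentence and a small departure from the protocol wording. No new measurements are needed, provided all three individual readings are entered in the database and not only the derived value; this should be confirmed. If the team wants to know what the change is worth, the within-eye SD and the share of eyes with a third reading can be estimated from pooled masked data.

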#### 14.2.4 CONJUNCTIVAL REDNESS

The Ora Calibra® Conjunctival Redness Scale for Dry Eye will be performed on all scheduled visits. Both pre- and post-CAE® assessments will be made at Visits 1, 2, 4, 5, and 6. The conjunctival redness scale ranges from 0 to 4 [REDACTED]

[REDACTED]  
[REDACTED]  
[REDACTED].

Scores will be summarized by visit, time point, and treatment group using quantitative summary statistics, including 95% confidence intervals. Change from baseline will also be summarized. Study eye and fellow eye will be summarized separately. Pairwise two-sample t-tests will be employed to compare treatment and placebo means at each visit. Comparisons between treatment groups and between all active groups and placebo will also be conducted. The differences in means, two-sided 95% confidence intervals (CIs) for the difference in means and p-values will be reported. Wilcoxon rank sum tests will also be conducted. Analyses will be performed on the ITT population with observed data only.

Changes from baseline will be compared between treatment groups using ANCOVA models that adjust for baseline and site. The differences in means, two-sided 95% confidence intervals (CIs) for the difference in means and p-values will be reported. T-tests and Wilcoxon rank sum tests will also be conducted. Analyses will be performed on the ITT population with observed data only.

